1.1. STUDY FLOW CHART

Study Plan Schematic

Procedure	Screening Phase Visits 1-2 (Week 1-2)		Active Phase Visits 3-14 (Week 3-14) Including a 1st confirmatory visit if healed before 12 weeks of treatment		2nd Confirmatory Visit Prior to Follow-up Phase Visit 15 (Week 15)	Follow-up Phase Visits 16, 17, 18 & 19 (Week 19, 23, 27 & 31)			
	Visit 1 (Week 1)	Visit 2 (Week 2)	Visit 3 (Week 3) Randomization	Visits 4-14 (Week 4-14) Study Endpoint at Week 14*	Visit 15 (Week 15)	Visit 16 (Week 19)	Visit 17 (Week 23)	Visit 18 (Week 27)	Visit 19 (Week 31)
Inclusion/Exclusion Criteria	X	X	X						
Informed Consent/HIPAA document	X								

VR-36 Health Survey Questionnaire	X			X*					
Lower Extremity Functional Scale Outcome Questionnaire	X	X		X					X
Charlson-Comorbidity Index	X								
Physical Exam	X			X*					
EKG	X			X*					
Vital Signs	X	X	X	X	X	X	X	X	X
Ankle-Brachial Index/Duplex Scan	X	X							
Debrided Tissue for genetic analysis (Weeks,1-9)	X	X	X	X					
Bacterial, Fungal Infection and Malignancy Evaluation	X								
Laboratory evaluation (hematology, renal, and liver function)	X								
Vapometer Readings@ (@If healed, readings recorded from point of closure + 4 months)				X@	X	X	X	X	X
Blood Sample for Timolol assay/Inflammatory markers(weeks 4,8,12)	X			X†					
Ulcer Assessment	X	X	X	X	X	X	X	X	X
Debridement († if needed)	X	X	X	X	X†	X†	X†	X†	X†
Ulcer Photography and Area Measurement	X	X	X	X	X	X	X	X	X
Offloading device	X	X	X	X	X	X	X	X	X
Randomization			X						
SOC + Timoptic-XE@ or SOC + non biologically active gel (hydrogel as placebo medication)			X	X					

SOC			X	X	X	X	X	X	X
Concomitant Medications and Adverse Events	X	X	X	X	X	X	X	X	X

4.3.1 Screening/Baseline Period (Visit 1, 2)

Subjects that meet all criteria of the study will be given an informed consent form to review and sign. Subjects will be required to complete all screening assessments within the 2 weeks prior to randomization and start of treatments.

Screening assessments and pre-treatment: A comprehensive history and physical exam along with a battery of tests) will be performed on each study applicant to assess eligibility during the screening phase. Those subjects with known drug allergy to Timoptic-XE® and those not meeting the exclusion criteria will not be enrolled.

- 1) Demographic information: gender, age, race.
- 2) Medical history: medical problems, surgeries, trauma, history of previous ulcers, amputations, characteristic and duration.
- 3) Comprehensive history and physical exam: vital signs, height, weight, Body Mass index
- 4) General health and lifestyle: smoking history, alcohol, drugs abuse.
- 5) Lower extremity exam: vascular – pedal pulses, color of skin, temperature, edema; dermatological – clinical description of the ulcer, fungal infection of skin and/or nails, skin integrity (calluses, dryness); musculoskeletal – foot deformities such as bunion, hammertoe, bony prominence, fat pad atrophy, altered gait; neurological – absence or presence of sensation with 5.07/10 Semmes-Weinstein monofilament, reflexes.
- 6) Non-invasive vascular study: ankle-brachial systolic pressure (ABI) and toe-brachial systolic pressure (TBI). In order to meet criteria, ankle-arm index must be equal to or greater than 0.8 and less than 1.4 or a toe-arm index is equal to or greater than 0.6.
- 7) Foot ulcer history (location, length of time, treatments used, pain, etiology of ulcer).
- 8) Laboratory: hematology, chemistry, EKG, microbiology and pathology HbA1c, pregnancy test (for women of childbearing ages), LFT, ESR, CRP and albumin.
- 9) Radiological imaging – plain foot and/or ankle films for baseline.
- 10) Subjects will be given the health-related quality of life survey, VR-36 Health Survey and the Lower Extremity Functional Scale Outcome Questionnaire.
- 11) Sharp debridement of ulcer will be performed per standard method. A small sample will be collected for microbiology (gram stain, cultures/sensitivities, and fungal) and pathology.
- 12) Photographs of ulcer will be obtained before and after debridement using Silhouette Mobile™ ulcer tracing, surface area calculation.
- 13) Dressings applied will include non-adhesive dressing (Adaptic® or Mepitel®) over wound bed, covered by dry dressings.
- 14) Off-loading shoes will be given, modified offloading insert (trilaminar plastazote) as determined appropriate per discretion of clinician.

4.3.2 Randomization/Treatment (Visit 3/Week 3)

Those subjects that meet all eligibility criteria will be randomly assigned to one of the three groups. A randomized number will be assigned to each subject participating in the study, where one will receive either SOC+Timoptic-XE or SOC + non biologically active gel (hydrogel as placebo medication) or the control (standard therapy).

Patients that are not randomized into group A or B due to ineligibility (i.e. meet exclusion criteria, do not meet all inclusion criteria, non-compliance, withdrawal) will be passively followed via CPRS on the status of their diabetic foot ulcers for the duration of the study.

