PROTOCOL SUMMARY

TITLE OF THE STUDY: MERIT: Beta Adrenergic Antagonist For The Healing of Chronic Diabetic Foot Ulcers

Start Date: 04/01/2017
Ending Date 12/31/2024

PHASE: 2

METHODOLOGY: It is a prospective, randomized, double blinded, controlled, and parallel-group study with 2 arms. Follow up cohort will include a real-world group.

STUDY DURATION: 31 weeks

TREATMENT PHASE: 12 weeks

FOLLOW-UP PHASE: 16 weeks

REAL-WORLD GROUP: 12 weeks

STUDY CENTERS: One centralized study location Multispecialty Wound Healing Clinic at Sacramento VA Medical Center.

Note: Primary Care, Vascular, Podiatry and Dermatology clinics from the at the Veteran Affairs Northern California Health Care System (VANCHS) satellite clinics (Redding, Chico, Martinez, Oakland, McClellan, and Fairfield) will refer patients to the study location.

NUMBER OF SUBJECTS: 2 treatment arms, 24 subjects per arm for a total of 48; Screen-failed patients to be followed passively on the status of their diabetic foot ulcer via CPRS. Additional patients will be screened and enrolled for exploratory follow up to study inflammatory markers in non-healing patients.

STUDY OBJECTIVES: The primary objective of this study is to assess the effectiveness of the topically applied Timoptic-XE® or timolol (a non-selective beta adrenergic receptor antagonist (β BAR)) versus standard of care for the treatment of non-healing diabetic foot ulcers. The primary endpoint will be the measurement of the complete ulcer closure (as defined by “skin re-epithelialization without drainage or dressing requirements) at 12 weeks. The secondary outcomes will be the following: comparison of percent difference change in size from the randomization visit to the endpoint visit (post 12 weeks) between the treatment and control group, the time to wound closure between the two groups, and wound healing rates with impact of wound size between the treatment groups, change in trans-epidermal water loss measurements at sites of healed wounds, measurement of quality of life using Veterans Rand (VR-36) Health Survey, measurement of the Lower Extremity Functional Scale Outcome and the Charlson Comorbidity Index.

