24. Prisoners, institutionalized individuals or vulnerable population
(The real-world group will not have any exclusion criteria related to timolol (criteria 18-22)

(*)Note: The exclusion criteria were modified compared to the original submission based on the recommendation from the DMC, which suggested that these criteria would significantly impair the enrollment. Those were also revised upon evaluation by the consultant Cardiologist, [name].

TREATMENT: Total duration of study per subject: Up to 31 weeks (Includes to 2 weeks of screening and up to 16 weeks until the end of the follow-up period). 12 weeks for the real-world group.

DURATION OF ADMINISTRATION: Daily application for 12 weeks (starting at Visit 3/Week 3).

STUDY DESIGN: This is a prospective, randomized, double blinded, controlled, and parallel-group study with 2 arms: β AR antagonist (SOC plus topically applied Timoptic-XE®) and control (standard of care (SOC) plus non-biologically active gel (hydrogel, Kendall®, placebo medication)).

EFFICACY ENDPOINTS:**PRIMARY EFFICACY OUTCOME**

1. Complete closure of ulcer by Visit 14/Week 14

SECONDARY EFFICACY OUTCOME

1. Complete closure of ulcer by Week 31
2. Percent difference change in size from the randomization visit to the endpoint visit (post 12 weeks)
3. Time to wound closure
4. Rate of ulcer healing
5. Change in transepidermal water loss of re-epithelialized wound after wound closure

SAFETY ENDPOINT:**PRIMARY SAFETY OUTCOME**

1. Timolol serum levels during the treatment phase

SECONDARY SAFETY OUTCOME

1. Mean changes from baseline in systolic and diastolic blood pressure in mmHg
2. Mean changes from baseline in heart rate in beats per minute
3. Adverse events associated with the use of timolol.

QUALITY OF LIFE ASSESSMENT: We will use ANCOVA to analyze the quality of life from the VR-36 Health Survey and the Lower Extremity Functional Scale Outcome Questionnaire.

DATA ANALYSIS:

The primary outcome is complete ulcer closure by Week 12 (end of the Active Phase) of the study and the rate of ulcer healing by the 12th week of care between the two arms.

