For demographic and clinical characteristic data at baseline, continuous variables will be summarized (when appropriate) by using mean, median, standard deviation, co-efficient of variation, minimum value and maximum value. Categorical variables will be summarized with frequency tables. Baseline comparability between the two treatment groups will be assessed by using the independent two-sample t-test or Wilcoxon rank-sum test and the Chi-square test or Fisher's exact test.

Following wound closure, comparison of changes in the epidermal barrier function of healed ulcers treated with timolol vs those treated with saline control will be non-invasively measured quantitating the transepidermal water loss (TEWL). Categorical variables will be summarized with frequency tables. Baseline comparability between the two treatment groups will be assessed by using the independent two-sample t-test or Wilcoxon rank-sum test and the Chi-square test or Fisher's exact test.

TABLE OF CONTENTS

- 1 BACKGROUND AND RATIONALE
- 2 OBJECTIVES
- 3 STUDY POPULATION
- 4 STUDY PROCEDURES
 - 4.1 DESIGN AND METHODOLOGY
 - 4.2 DESCRIPTION OF STUDY GROUPS
 - 4.3 STUDY FLOW CHART
 - 4.3.1 SCREENING/BASELINE PERIOD (VISIT 1 to 2/WEEKS 1 to 2)
 - 4.3.2 RANDOMIZATION (VISIT 3/WEEK 3)
 - 4.3.3 TREATMENT PHASE (VISIT 4/WEEK 4)
 - TREATMENT PHASE (VISIT 5/WEEK 5)
 - TREATMENT PHASE (VISIT 6/WEEK 6)
 - TREATMENT PHASE (VISIT 7/WEEK 7)
 - TREATMENT PHASE (VISIT 8/WEEK 8)
 - TREATMENT PHASE (VISIT 9/WEEK 9)
 - TREATMENT PHASE (VISIT 10/WEEK 10)
 - TREATMENT PHASE (VISIT 11/WEEK 11)
 - TREATMENT PHASE (VISIT 12/WEEK 12)
 - TREATMENT PHASE (VISIT 13/WEEK 13)
 - TREATMENT PHASE (VISIT 14/WEEK 14)
 - 4.3.4 STUDY ENDPOINT (VISIT 14/WEEK 14)
 - 4.3.5 2ND CONFIRMATORY VISIT (VISIT 15/WEEK 15)
 - 4.3.6 FOLLOW-UP PHASE (VISIT 16/WEEK 19)
 - FOLLOW-UP PHASE (VISIT 17/WEEK 23)
 - FOLLOW-UP PHASE (VISIT 18/WEEK 27)
 - FOLLOW-UP PHASE (VISIT 19/WEEK 31)
 - 4.3.7. REAL-WORLD GROUP PHASES
 - SCREENING/BASELINE PERIOD (VISIT 1/WEEK1)
 - FOLLOW-UP PHASE (VISIT 2/WEEK 6)
 - STUDY ENDPOINT (VISIT 3/WEEK12)
 - 5 ADVERSE EVENTS
 - 6 STATISTICAL DESIGN
 - 7 APPENDIX 1 – Wound scoring system
 - 8 APPENDIX 2 – Hemostasis procedure
 - 9 APPENDIX 3 – Infection exclusion procedure
 - 10 APPENDIX 4 – Home Care Instructions

- 11 APPENDIX 5 – Veterans Rand-36 (VR-36) Health Survey**
- 12 APPENDIX 6 – Lower Extremity Functional Scale**
- 13 APPENDIX 7 – Charlson Comorbidity Index**

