Each subject will be given a unique identifier that will have no personal information linked after assignment of a randomly computer-generated list of three repeated numbers which will be available. The request for assignment will be emailed to the Data Coordinator with a completed eligibility form, and no personal identifiers except for initials and a last 4 digits of social security. The Data Manager will assign a number and the next sequential group assignment with each subsequent request will be placed in sealed envelopes. These sealed envelopes will be provided to the pharmacist will dispense the Timoptic-XE® or non-biologically active gel hydrogel for the patients according to the arm to which they have been randomized. Subject demographics will not be provided until this assignment is complete. Participants will be randomly placed into Group A (SOC plus Timoptic-XE®) or Group B (SOC plus non-biologically active gel). There will be an estimated of 24 patients in each group. The patients will not be informed of treatment administered.

Withdrawal:

The subjects may withdraw from the study at any time during the study, upon request. The investigator may also discontinue a subject if it is determined that the subject has not responded to therapy or adverse event occurred, which requires alternative therapy, or the patient displays non-compliance with study schedule. Those subjects that have undergone treatment will be followed and documented until end of the study. If there is more than 10 percent loss to follow-up, then investigators will attempt to recruit additional subjects.

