4. STUDY PROCEDURES

4.1 DESIGN AND METHODOLOGY

We propose a prospective, randomized, double blinded, controlled, and parallel-group study with 2 arms to assess the effectiveness of the topically applied Timoptic-XE® or timolol (a non-selective beta-adrenergic receptor antagonist) versus standard of care for the treatment of non-healing DFU in the VA system.

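### Relative ulcer area at Week 12 is compared without baseline area as a covariate: a cheap gain on one secondary endpoint, with a wording correction due in Section 4.3.2

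*Combined protocol and SAP*

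**What the plan says.** **Area analysis.** The Protocol Summary (Data Analysis) and Section 6 (Analyses) both plan a two-sided t-test or Wilcoxon rank-sum test, whichever is appropriate, for ulcer area at Week 12 relative to baseline. No covariate is named. ANCOVA is planned only for the questionnaires and the Charlson index. Wound size otherwise enters through chi-square or Fisher comparisons of healing rates and through secondary logistic regression; neither adjusts the area comparison. Inclusion criterion 2b admits ulcers of 0.5 to 20 cm², measured by Silhouette at randomisation. Sections 3 and 6 specify simple allocation.

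**Number of groups.** Section 4.3.2 says "Those subjects that meet all eligibility criteria will be randomly assigned to one of the three groups". After timolol it lists "SOC + non biologically active gel (hydrogel as placebo medication) or the control (standard therapy"), as if these were two destinations. Its next paragraph speaks of "Patients that are not randomized into group A or B due to ineligibility". The other sections have two arms:
- Protocol Summary, Number of Subjects: "2 treatment arms, 24 subjects per arm for a total of 48"
- Protocol Summary, Study Design: "parallel-group study with 2 arms: β AR antagonist (SOC plus topically applied Timoptic-XE®) and control"
- Section 3: "Participants will be randomly placed into Group A (SOC plus Timoptic-XE®) or Group B (SOC plus non-biologically active gel")
- Section 4.1: "parallel-group study with 2 arms to assess the effectiveness"

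Dispensing (Section 4.2) and the sample size (Section 6) also provide for two arms only. The transepidermal water loss text in the Protocol Summary gives the comparator yet another name: "healed ulcers treated with timolol vs those treated with saline control".

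**The concern.** Dividing by baseline puts ulcers on a common scale, but it need not remove a dependence of relative change on initial size: large ulcers may shrink proportionally more slowly than small ones. The permitted entry range is 40-fold (20 / 0.5), although the enrolled distribution may be narrower. With 24 per arm and simple allocation, the arms can differ noticeably in baseline area by chance. If size is prognostic, an unadjusted comparison leaves explainable variation in the error term and does not correct for such an imbalance. The plan itself lists healing in relation to wound size as a secondary outcome, so it already regards size as possibly prognostic. At stake is the precision of one secondary comparison.

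The group wording matters for a different reason. Section 4.3.2 is where a reader looks to learn how subjects are assigned, and it names a destination that the allocation, dispensing and analysis sections do not have.

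**Working it through.** **1. The plan's own figure.** Inputs from Section 6, Sample Size Estimation: 20% versus 63% closure, two-sided Fisher's exact test, 5% level, 80% power, 24 per arm. Full enumeration gives power of 79.5% at 23 per arm and 82.5% at 24. So 24 per arm is reproduced, for two arms. Expected closures are 24 × 0.20 + 24 × 0.63 = 4.8 + 15.1 = 19.9 of 48, so about two fifths of the relative areas would be exactly zero. That many ties favours a rank method.

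**2. Chance imbalance.** With 24 per arm, the difference in mean log baseline area has SD √(2/24) = 0.289, in units of the between-subject SD. Under normality, P(|difference| > 0.5 SD) = P(|Z| > 0.5/0.289 = 1.73) = 8.3%.

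**3. Power simulation.** There are 24 per arm and 20,000 trials per cell. Relative area is a latent normal value, set to zero below the closure threshold. The threshold gives 20% closure in control, and a shift of the whole timolol distribution gives 63% or 45%. The 45% is an assumed smaller effect. *r* is the correlation of log baseline area with the latent value; the documents give none, so 0 to 0.5 is assumed. The Wilcoxon test is tie-corrected with a normal approximation. The rank ANCOVA regresses the rank of relative area on treatment and the rank of baseline area.

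| Closure | r | Wilcoxon | Rank ANCOVA | Change (points) |
|---|---|---|---|---|
| 63% vs 20% | 0 | 95.6% | 95.3% | -0.3 |
| | 0.3 | 95.4% | 96.4% | +1.0 |
| | 0.5 | 95.7% | 98.3% | +2.6 |
| 45% vs 20% | 0 | 63.0% | 62.2% | -0.8 |
| | 0.3 | 63.0% | 66.1% | +3.1 |
| | 0.5 | 62.8% | 72.4% | +9.6 |

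**4. Sensitivity.** Here closure is independent of baseline area, *r* applies only among ulcers still open, and open ulcers are shifted by an assumed 0.5 SD.

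| Closure | r | Wilcoxon | Rank ANCOVA | Change (points) |
|---|---|---|---|---|
| 63% vs 20% | 0 | 91.5% | 90.9% | -0.6 |
| | 0.3 | 91.9% | 91.8% | -0.1 |
| | 0.5 | 91.8% | 92.4% | +0.6 |
| 45% vs 20% | 0 | 63.1% | 62.5% | -0.6 |
| | 0.3 | 63.0% | 63.5% | +0.5 |
| | 0.5 | 63.7% | 65.3% | +1.6 |

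**5. Type I error (20% closure in both arms).** Over all trials, the rank ANCOVA gives 4.8%, 5.2% and 5.0% at r = 0, 0.3 and 0.5. The planned Wilcoxon also stays at about 5%. Only within the 8.3% of trials with an imbalance above 0.5 SD do they part: Wilcoxon 8.5% against rank ANCOVA 5.2% at r = 0.3, and 15.2% against 5.5% at r = 0.5.

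**6. The third group.** Group C (Section 4.2) is passive follow-up of patients who were not randomised, and Section 2 describes the real-world cohort as not randomised. Neither can be a randomised third group. Sections 4.2 and 4.3.3 treat hydrogel as part of standard of care, so no separate randomised standard-therapy arm is defined anywhere.

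**The case against.** The strongest reply on the area analysis is that nothing is broken. Randomisation makes the unadjusted test valid, the endpoint is already scaled to baseline, and the endpoint is secondary. At the plan's own effect the Wilcoxon test already has about 95.6% power. All of this stands. The +10 points needs both an assumed smaller effect and the top of an assumed correlation range.

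A reader might infer from the 15.2% in step 5 that the planned test inflates false positives. It does not: that figure is conditional on a large imbalance and on r = 0.5, and over all trials the level holds.

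A second fair objection is that a rank ANCOVA coefficient is not in percent area, whereas the endpoint is percent change in size. That is a real cost, and the fix has to meet it with a separate estimate.

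On Section 4.3.2, a reader might infer a three-arm trial with 48 / 3 = 16 per group, for which exact Fisher power would be 57.8%. The documents do not support this: allocation, dispensing and sample size provide only for Groups A and B. The count of three may come from the three labelled groups in Section 4.2, and standard therapy may simply rename the hydrogel arm. Either explanation leaves the sentence wrong, since Group C is not randomised, but neither makes it more than a text error.

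**Conclusion.** The area comparison is valid but can be made somewhat more precise, and better protected against chance imbalance, with a covariate already measured. Across the assumed correlations of 0 to 0.5, the change in power is about 0 to +3 points at 63% versus 20%, about -1 to +10 points at 45% versus 20%, and about -1 to +2 points if closure is unrelated to baseline area. These figures rest on the assumed correlation, the latent-normal model and 24 analysed per arm. This is a worthwhile low-cost improvement, not a correction of an error. No fault is found with simple allocation, the primary test or the sample size.

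The contradiction in Section 4.3.2 is certain as a matter of text, but it changes no power figure or result. That it is left over from another design is plausible but only an inference.

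**What to change.** 1. In Section 6 (Analyses) and the matching Protocol Summary text, before unblinding, replace the unadjusted t-test or Wilcoxon comparison of relative ulcer area at Week 12 with a rank-based ANCOVA on treatment and Silhouette area at randomisation. State that closed ulcers enter as zero. Report the median percent change per arm and a between-arm difference, for example Hodges-Lehmann, so that the effect can be read in percent area. Leave the primary Fisher test as it is.

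2. Reconcile Section 4.3.2 with the two-arm design: assignment to Group A or Group B, with no separate standard-therapy destination. Use one name for the hydrogel comparator throughout, including where the water-loss text calls it saline.

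Cost: one covariate already collected, one added estimate and a few words. If baseline area is not prognostic, up to about 1 point of power is lost on this endpoint. The test is on the rank scale, so the separate effect estimate is required. The allocation list, visits and sample size are unchanged.

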4.3.3 Treatment Phase (Visits 4 to 14/Weeks 4 to 14)

Subjects will be evaluated and receive treatments on weekly basis (7 days +/- 2 days).

Appointments will be made as determined by investigator at each VA facility.

- All subjects will have weekly visit including:
 - Vital signs
 - Ulcer assessment and measurement
 - Lab tests per protocol
 - Sharp debridement
 - Weeks 1-9: debrided tissue will be collected and analyzed for molecular markers of inflammatory characterization of wound microbiome.
 - Wound cleansing and moist wound healing dressing
 - Infection assessment if indicated with confirmatory bacterial culture (deep swab curette, tissue specimen/biopsy), radiographical X-rays and blood work (CBC, ESR, CRP, and chemistry) if deemed necessary by investigator clinician.
 - Use of an offloading device that protects the wound from pressure or trauma related to ambulation and other acts of daily living. The total contact cast or instant total contact cast would be ideal offloading devices. However, given the nature and complexities associated with DFU, it is unrealistic to expect that all patients to tolerate such offloading devices. Thus, the offloading device provided will be dependent on the subjects' ability to tolerate the specific offloading device. Adherence to offloading device will be evaluated by the investigator at each visit by observing plantar wear patterns and inquiring from the patient if offloading was used consistently as instructed. Alternative to total contact cast or instant total contact cast (cam walker), offloading devices will be offered including, but not limited to the use of felt/foam adhesive/post op shoe, custom offloading insole, and customized healing shoe in combination with gait assistive device such as a roll-a-bout scooter, walker, wheelchair or motorized scooter.
 - Application of treatments:
 - Standard of Care: Application of non biologically active gel (hydrogel as placebo medication), non-adhesive dressing (Adaptic® or Mepitel®), over wound bed, covered by dry gauze dressings
 - Timoptic-XE®: Application of Timoptic-XE®, non-adhesive dressing (Adaptic® or Mepitel®), over wound bed, covered by dry gauze dressings. Up to 12 weeks of daily applications will be done to wound until healed.
 - Offloading devices (see above)

- Changes in concomitant medications, adverse events, compliance to offloading, will be recorded.
- If ulcers heal sooner than 12 weeks, the subject will be assessed the following week for a confirmatory visit, followed another week later by a 2nd confirmatory visit. Ulcer healing is defined by 100% epithelialization as determined by the clinician. The subject with healed ulcer will also return for follow-up visits Weeks 19, 23, 27 & 31 (visits 16, 17, 18 and 19).
 - Vapometer recordings will be collected on visits corresponding to weeks 19, 23, 27, and 31 on the newly healed ulcer site, 5 cm away from healed ulcer site. Readings on the contralateral side will also be marked and taken and recorded. **5 recordings for each site will be taken and the average will be documented.

NOTE: if ulceration remains open after the 12th week of application – then will switch back to standard of care and the subject will be followed monthly until completion of the study.

Blood samples will be taken on each subject on weeks 4, 8 and 12 to determine serum Timolol level. We do not anticipate blood levels in our patients to be higher than those seen in patients who receive Timoptic XE® gel for ocular indication (normal range: 0.3-0.5 ng/ml). We will terminate study on patients in whom Timolol level is 0.7 ng/ml or higher.

